## Background

Tinnitus, characterized by the perception of sound in the absence of an external stimulus, is one example of such a condition. Managing tinnitus is notoriously challenging as there is often not a curable medical cause. The intervention with strongest research evidence is cognitive behavioral therapy (CBT) for tinnitus. CBT is psychological intervention addressing unhelpful thought patterns and emotional reactions caused by tinnitus (Andersson, 2002). Despite the evidence base, accessibility to CBT for tinnitus is limited due to a dearth of healthcare providers with the knowledge and expertise to provide CBT to this population (Bhatt et al., 2016; Henry et al., 2019). However, no previous trials on Spanish population exist.

## Objectives

The aim of the present study was to run a small-scale study to inform feasibility of ICBT in Spanish to inform the protocol of a implementing a larger randomized clinical trials (RCT). The specific objects were to investigate the recruitment, compliance, engagement, acceptance, and outcome feasibility in reducing tinnitus distress and tinnitus associated problems, using ICBT for Spanish speakers with tinnitus.

## Study Design

A single-group pretest posttest design was used to determine the feasibility of ICBT for Spanish communities and refine the protocol for larger studies. This was intended to be an initial small-scale study ( $n = 32$ ) without a control group to test the protocol prior to allocating resources to a larger scale study. Such studies are an important initial part of clinical trials designs for complex interventions and considered as the Phase 1 trial.

## Intervention

The ICBT intervention content was based on a CBT self-help program originally developed in Swedish (Andersson & Viktor, 2004). This intervention has been translated into German (Jasper et al., 2014) and English (Abbott, et al., 2009) and adapted into an interactive 8-week interactive e-learning version (Beukes, et al., 2016). For the purposes of this study the intervention was translated into Spanish, ensuring readability at below the recommended 6th-grade level (Beukes, et al., 2020) and functionality of the platform housed in the US was established (Manchaiah, et al., 2020a). The ICBT program employed 22 modules with videos, worksheets and quizzes (Beukes et al., 2021a).

To minimize the resources required, on-support guidance was offered to participants. There was an encrypted two-way messaging system enabling participants to ask questions about the program. These messages were monitored by a Spanish-speaking doctoral audiology student who responded in Spanish. If required, further support was available from a specialist tinnitus audiologist or a licensed CBT therapist.

## Outcome Measures

The primary outcome was Tinnitus severity as measured by the Tinnitus Functional Index (TFI) (Meikle et al., 2012). Secondary outcomes included measures of anxiety, depression, insomnia, tinnitus cognitions, hearing-related difficulties, and health-related quality of life. Spanish translations (Manchaiah et al., 2020b) of all outcome measures are listed below.

### ***Primary Outcome Measure***

The primary outcome measure was tinnitus severity as measured by the TFI (Meikle et al., 2012). It was selected over other tinnitus questionnaires as it was specifically developed to measure tinnitus severity and assess responsiveness to treatment and for comparison purposes with similar trials in the UK and the US (Beukes et al., 2017, 2018, 2021b).

### ***Secondary Outcome Measures***

The following secondary measures were incorporated to assess commonly reported tinnitus-related difficulties:

- The Generalized Anxiety Disorder-7 (GAD-7; Spitzer et al., 2006) assessed symptoms of generalized anxiety disorder.
- The PHQ-9 (Spitzer, Kroenke, Williams, 1999) indicated symptoms of depression.
- The Insomnia Severity Index (ISI; Bastien, Vallières, & Morin, 2001) assessed the presence of insomnia.
- The Tinnitus Cognitions Questionnaire (TCQ; Wilson & Henry, 1998) was used to measure negative tinnitus cognitions.
- The EQ-5D-5L (Herdman et al., 2011) measured general health-related quality of life.
- The Tinnitus and Hearing Survey (THS; Henry et al., 2015) was used as a short measure to identify participants' tinnitus severity, hearing disability, and hyperacusis.

To monitor participants tinnitus severity while undertaking the intervention, the screening version of the Tinnitus Handicap Inventory (THI-S; Newman et al, 2008) was completed weekly during the course of the 8 week intervention. If scores increased by more than 10 points between two consecutive weeks, the participant was contacted to discuss presenting difficulties.

Participants were also monitored weekly by a newly developed Tinnitus Qualities Questionnaire (TQQ; Beukes et al., 2021a). The TQQ measures psychoacoustic tinnitus qualities such as pitch, loudness, and the number of tones heard.

Online questionnaires were used throughout the study. All the measures were completed pre- and post-intervention, and at two-month follow-up. To maximize retention, 3 electronic reminders were sent to participants who had not completed questionnaires.

### **Recruitment**

We aimed to recruit participants across the globe without any geographical barrier. To recruit Spanish speakers, a range of strategies were used to disseminate information, including social media (Facebook and Twitter), emails, forums. As uptake was low a company "TrialFacts" were contracted to boost recruitment. The main recruitment period was between 1 March to 20 April 2020. Those interested were directed to the study website, where all the information was available to read in Spanish regarding what the study entailed and how to register. Study eligibility was determined as follows:

- Spanish speakers, adults, aged 18 years and over from any location;
- Access to a computer, the internet and the ability to email;
- Experiencing tinnitus for a minimum period of three months;
- A tinnitus severity score of 25 or greater on the TFI indicating the need for an intervention;

- Not undertaking any other therapies or interventions that may interfere with the current study; and
- Not presenting with any serious health conditions that may prevent undertaking the intervention.

### **Statistical Analysis Plan**

Statistical analyses were performed using the Statistical Package for Social Sciences (SPSS) version 26.0. The study outcomes of interest were retention, feasibility, and effect size at post-intervention. For all analyses, the goal of this pilot was to estimate the pre-post-test effect size for all primary and secondary outcomes; however 2-sided  $p$ -values using alpha = 0.05 are also reported. Missing data were handled through multiple imputation using the Markov Chain Monte Carlo approach as they were missing at random (Little's MCAR test  $X^2 = 17.50$  (24) = .83). For comparison purposes a completer's only analysis was also done. The data that support the findings of this study are openly available in Figshare at <http://doi.org/10.6084/m9.figshare.13718896>.

### **Effect Sizes and Statistical Modelling**

Effect sizes (Cohen's  $d$ ) at post-intervention were calculated by dividing the differences in pre- and post-intervention means by the pooled standard deviations. The reliable change index (RCI) (Jacobson & Truax, 1991) was used as a means of calculating clinical significance for the TFI as the primary outcome. This was calculated using the mean pretest posttest score difference, the pre-intervention standard deviation, and a test-retest reliability coefficient of 0.78, and as reported in the validation study (Meikle et al, 2012). Finally, linear mixed models (LMM) using maximum likelihood with random intercept for participants were used to account for repeated measures and incorporate all available data points in the analysis. The models were used to determine the effect of the pre-intervention scores on follow-up scores. The LMM induces a scaled identity covariance structure. Bonferroni-corrected pairwise post hoc tests were applied to determine which timepoints were significantly different, for each variable.

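### The pilot's main estimate is Cohen's d without a small-sample correction; at n = 32 its magnitude is overstated by about 1 to 2.5% on average

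*Combined protocol and SAP*

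**What the plan says.** The combined protocol and SAP, under Effect Sizes and Statistical Modelling, defines Cohen's d at post-intervention as obtained "by dividing the differences in pre- and post-intervention means by the pooled standard deviations". It does not write out how the pooled standard deviation is formed from paired measurements, and it names no correction factor.

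Under Statistical Analysis Plan, the effect size is the central quantity: "the goal of this pilot was to estimate the pre-post-test effect size for all primary and secondary outcomes". Two-sided p-values accompany it. Missing values are multiply imputed, and a second analysis drops incomplete cases: "For comparison purposes a completer's only analysis was also done". The number of completers is not given.

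Under Study Design: "This was intended to be an initial small-scale study ( $n = 32$ ) without a control group". The documents contain no value of d, no outcome mean or standard deviation, and no pre/post correlation.

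**The concern.** A sample standard deviation varies around its population value, and the average of its reciprocal exceeds the reciprocal of the true value. A mean difference divided by it is therefore, on average, too large in magnitude, and the more so the smaller the sample. The excess is multiplicative and has the same relative direction for every outcome with a true change, so it does not average out across outcomes.

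What is at stake is modest. This statistic is the one the pilot sets out to estimate. The plan also puts two versions of it side by side, imputed and completers only, and the bias is larger in whichever uses fewer people. The TFI was chosen partly for comparison with similar UK and US trials, and an estimator whose bias depends on n suits that less well than one whose bias has been removed.

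**Working it through.** The plan states no effect size, so there is no figure to reproduce. The check is on the estimator itself.

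**Inputs.** From the documents: n = 32, a single group measured before and after, and d = (mean pre - mean post) / pooled SD. Assumed: the pooled SD is the root mean of the pre and post variances; normal data; pre/post correlation r from 0 to 0.9, with 0.3 to 0.7 as the central range; true d from 0 to 1.0, with 0.8 as the worked case; 20 completers for the smaller analysis.

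**Step 1: bounds.** The factor that removes the bias is J(df) = Γ(df/2) / [√(df/2) · Γ((df - 1)/2)], approximately 1 - 3/(4·df - 1). The average inflation is 1/J - 1. The pooled SD of paired data carries between n - 1 degrees of freedom (r = 1) and 2(n - 1) (r = 0).

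| n | df | J | inflation |
|---|---|---|---|
| 32 | 31 | 0.9756 | 2.50% |
| 32 | 62 | 0.9878 | 1.23% |
| 20 (assumed) | 19 | 0.9599 | 4.18% |
| 20 (assumed) | 38 | 0.9801 | 2.03% |

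**Step 2: between the bounds.** For paired data df = 2(n - 1)/(1 + r²). At n = 32:

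| r | df | J (approximate formula) | inflation | simulated at d = 0.8 |
|---|---|---|---|---|
| 0.3 | 62/1.09 = 56.9 | 0.9868 | 1.34% | 1.37% |
| 0.5 | 62/1.25 = 49.6 | 0.9848 | 1.54% | 1.49% |
| 0.7 | 62/1.49 = 41.6 | 0.9819 | 1.85% | 1.78% |

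The last column simulates the plan's own formula with 200,000 replicates. It agrees with the df formula to within simulation error. At n = 20 the simulated values for the same correlations are 2.12%, 2.53% and 3.05%.

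**Step 3: size against noise.** On d = 0.8 the excess for r = 0.3 to 0.7 is 0.8 × 0.0137 = 0.011 to 0.8 × 0.0178 = 0.014. At the df = 31 bound it is 0.8 × 0.025 = 0.020. The simulated standard error of d at n = 32 and d = 0.8 falls from 0.27 (r = 0) to 0.13 (r = 0.9). Over all scenarios run at n = 32 (d from 0 to 1.0, r from 0 to 0.9) the bias never exceeded 0.022, or 0.15 standard errors. At true d = 0 there was none.

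**Step 4: which df to use.** The simpler choice df = n - 1 = 31 removes too much: 1.0137 × 0.9756 = 0.989 at r = 0.3 and 1.0178 × 0.9756 = 0.993 at r = 0.7, so d would end up 1.1% to 0.7% too small. With df = 2(n - 1)/(1 + r²) the simulated bias disappears and the root mean squared error falls slightly.

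**The case against.** The strongest objection is that this does not matter. The excess is in the second decimal, well inside the sampling error, and would alter no reading of the pilot. Means and standard deviations are to be reported at each time point and the data are public, so a reader could make the conversion (r would come from the data set). All of that stands. It limits the point to a minor improvement but does not remove it, because the team holds everything needed and the quantity is the study's stated goal.

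A second objection is that r is not in the documents and the right df for imputed data is unclear. The first half falls away, because r can be computed from the collected data. The second half has some force: J computed within an imputed data set treats imputed values as observed. The possible error is small. At r = 0.5, J is 0.985 for n = 32 and 1 - 3/(4 × 30.4 - 1) = 0.975 for n = 20, a gap of about 1%.

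Two stronger readings are tempting, and neither is supported.

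- A reader might infer that every outcome's effect is biased upward. The bias is away from zero and proportional to the true effect. It is nil where nothing changes, and it makes a negative pre-minus-post effect more negative. It is also a property of the average, not of any one observed d, and the documents report no d that could be shown to be wrong.
- A reader might infer that a later trial sized from this d would be about 3 to 4% too small, since N varies as 1/d² and 1.014² = 1.028, 1.018² = 1.036. Squaring the average bias is not valid, because 1/d² is convex. In simulation (n = 32, d = 0.8, r = 0.3 to 0.7) the median derived N is 0.986 to 0.992 of the correct N, so 0.8 to 1.4% too small. After correction it is about 2% too large. The 5th to 95th percentiles run from about half to two or three times the correct N. Nor does the plan say that this d will size a trial, and a single-group pre/post d is not a between-group effect.

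**Conclusion.** The point holds as a minor one. The plan's main estimate is uncorrected Cohen's d, which at n = 32 is on average too far from zero by 1.2 to 2.5%, and by about 1.4 to 1.8% if the pre/post correlation is 0.3 to 0.7. With 20 completers it would be about 2 to 4%. These figures rest on approximate normality, on a pooled SD taken as the root mean of the two variances, and on assumed correlations and completer numbers that the documents do not give. The existence and direction of the bias, given a true change, do not depend on the assumed correlation or completer number. No conclusion of the pilot is put in doubt.

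**What to change.** Report Hedges' g in place of Cohen's d, or beside it, for each outcome:

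- State the pooled SD formula, for example the root mean of the pre and post variances.
- Compute g = J × d with J = 1 - 3/(4·df - 1) and df = 2(n - 1)/(1 + r²), where r is the observed pre/post correlation of that outcome and n is the number analysed. Do not use df = n - 1, which over-corrects.
- In the imputed analysis, apply the factor within each imputed data set and then pool. In the completers analysis, use the number of completers.

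A confidence interval beside g would also help, since the plan specifies none for d and sampling error is much the larger uncertainty.

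The cost is one multiplication per outcome from data already collected, and slightly smaller stated effects: at n = 32 a d of 0.80 becomes 0.79 at r = 0.3 to 0.5 (0.80 × 0.9868 = 0.789; 0.80 × 0.9848 = 0.788).

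### The reliable change index shows that a TFI change exceeds measurement error, not that it is clinically significant; report it as reliable change and cross-tabulate it against TFI below 25

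*Combined protocol and SAP*

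**What the plan says.** The Primary Outcome Measure section states: "The primary outcome measure was tinnitus severity as measured by the TFI". Under Effect Sizes and Statistical Modelling, the RCI "was used as a means of calculating clinical significance for the TFI as the primary outcome". On its ingredients the same section says: "This was calculated using the mean pretest posttest score difference, the pre-intervention standard deviation", together with "a test-retest reliability coefficient of 0.78". It gives no numeric threshold and no multiplier, and does not say whether the index is applied to each participant or to the group.

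The Recruitment section lists as an eligibility condition: "A tinnitus severity score of 25 or greater on the TFI indicating the need for an intervention". This is the only place where a TFI score is given a clinical meaning.

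No analysis section returns to the value 25 or names any other end-state score. The remaining TFI analyses (Cohen's d, the linear mixed model with pairwise comparisons, and means and SDs by time point) all concern group means.

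**The concern.** Reliable change and clinical significance are different claims. Reliable change says that a fall is unlikely to be measurement error alone. Clinical significance says something about the state the participant has reached. The RCI as described is built from a change score, a baseline SD and a reliability coefficient, so it can support only a claim of reliable change.

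A participant who starts high can therefore show reliable change and still score at or above the level that the plan treats as indicating need for an intervention. If that result is reported as clinical significance, it claims more than its inputs carry. The plan also produces no count of participants who end below 25. Because the Objectives section says the pilot is to inform a larger randomised trial, the label could pass into that trial's protocol.

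**Working it through.** **Figure to reproduce.** There is none. The plan states no RCI threshold and no proportion with reliable change.

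**Inputs from the plan.** Reliability r = 0.78 (Effect Sizes and Statistical Modelling); TFI entry cut-off 25 (Recruitment); n = 32 (Study Design).

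**Inputs assumed.** The baseline TFI SD, which the plan does not give, is taken as 10 to 25 points. The multiplier is taken as 1.96. The plan's two-sided alpha of 0.05 is consistent with that value, but the plan does not link it to the RCI. The index is assumed to be applied to each participant.

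**Step 1: threshold.** The standard error of a difference is SD × √2 × √(1 − r) = SD × √(2 × 0.22) = 0.663 SD. The threshold is 1.96 × 0.663 SD = 1.30 SD.

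**Step 2: comparison with the cut-off.** A fall of exactly the threshold leaves a participant at or above 25 whenever the baseline is at least 25 + 1.30 SD.

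| Assumed SD | Threshold (points) | Baseline from which a just-reliable fall still ends at 25 or more | End score after a just-reliable fall from 80 |
|---|---|---|---|
| 10 | 13.0 | 38.0 | 67.0 |
| 15 | 19.5 | 44.5 | 60.5 |
| 18 | 23.4 | 48.4 | 56.6 |
| 20 | 26.0 | 51.0 | 54.0 |
| 25 | 32.5 | 57.5 | 47.5 |

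**Step 3: an example at SD 18.** From 75 to 50 is a fall of 25, which exceeds 23.4, so it is reliable change. The end score is 50 / 25 = 2 times the cut-off. The criteria can also differ the other way: from 35 to 15 is a fall of 20, short of 23.4, although the end score is below 25.

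**Step 4: how many entrants have a baseline that high.** Suppose registrants' TFI is normal with mean 45 to 55 and SD 20 to 22, only those at 25 or above enter, and the SD among entrants sets the threshold. Then 56% to 69% of entrants start high enough that a just-reliable fall leaves them at 25 or more. This describes the baseline distribution. It is not an error rate, because it says nothing about how far participants actually fall.

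**Step 5: illustrative frequency of disagreement.** A simulation assumed a normal baseline limited to 25 to 100 (mean 45 to 65 and SD 15 to 25 before that limit, giving an entrant SD of 12.8 to 18.5), a mean fall of 10 or 20 points and a pre-post correlation of 0.6. Between 8% and 40% showed reliable change but stayed at 25 or above. Between 1% and 11% fell below 25 without reliable change. In a sample of 32 the first range is 0.08 × 32 = 2.6 to 0.40 × 32 = 12.8, or about 3 to 13 participants. These figures depend wholly on the assumptions.

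**The case against.** The strongest reply is that the plan makes no commitment that it then breaks. The value 25 is an entry criterion and nowhere a recovery threshold. The stated objectives are recruitment, compliance, engagement, acceptance and outcome feasibility, and the Statistical Analysis Plan section names retention, feasibility and effect size. None of these asks for an end-state proportion. This stands: using 25 as an end-state benchmark extends the plan.

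A second reply is that the plan refers to the mean difference, which may describe a group-level index. On that reading no participant is classified and the 75-to-50 example does not arise. This stands as a limit on the example. It does not rescue the label, because a group-level index contains no end-state score either.

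Third, the wording presents the RCI as one means among possible others. That is so, but no other criterion for clinical significance is given.

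Three stronger readings are tempting, and the documents do not support them:

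- A reader might infer that the plan counts participants as successes or responders. It defines neither, and no decision rule or progression criterion depends on the RCI.
- A reader might infer that the plan under-credits milder participants, such as the one going from 35 to 15. That is not a sound complaint: the fall is within what measurement error could produce at the assumed SD, and a rule requiring both criteria would exclude that participant too.
- A reader might take 56% to 69% as a misclassification rate. It is only the share of entrants for whom a just-reliable fall would leave the TFI at 25 or more, and the documents give no TFI mean or SD from which a rate could be estimated.

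**Conclusion.** The point holds in a limited form. The only stated criterion for clinical significance on the primary outcome measures reliability of change and is silent on end state. At every SD tried from 10 to 25, a participant who starts high enough can show reliable change while remaining at or above 25. This depends on per-participant use and the 1.96 multiplier, neither of which the plan states. How often it would happen cannot be determined from the documents.

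The importance is minor. The study is described as "an initial small-scale study ( $n = 32$ ) without a control group", its stated goal is effect-size estimation, and the effect sizes and mixed-model results are unaffected. What changes is what the pilot may say about clinical significance.

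**What to change.** 1. State that the RCI is applied to each participant, and give the multiplier and the resulting threshold in TFI points.
2. Report the result as reliable change, not as clinical significance.
3. At post-intervention and at the two-month follow-up, cross-tabulate reliable improvement against TFI below 25 and give the counts in four cells: both; reliable improvement but still 25 or more; below 25 without reliable improvement; neither.
4. Keep the term clinically significant for participants meeting both criteria. This also stops entrants just above 25 from qualifying through measurement noise. Say that 25 is carried over from the entry criterion as a benchmark.

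The cost is one extra table and a few sentences in the analysis plan. The TFI is already collected at both time points, so no new data are needed. The proportion called clinically significant can only stay the same or fall relative to the RCI alone, and will usually be lower. The change concerns analysis and labelling only.

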### **Sample Characteristics**

Descriptive statistics including gender, age, tinnitus duration, hearing aid use, and professionals consulted, were used to describe the sample. The mean and standard deviation were reported for each outcome measure at each time point. Descriptive statistics were also used to describe intervention adherence and engagement including the number of logins and modules read.

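### The TFI reliable change index is defined on the mean change, with no cut-off or participant counts, so as written it cannot show how many participants reliably changed

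*Combined protocol and SAP*

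**What the plan says.** Under Effect Sizes and Statistical Modelling, the RCI is "used as a means of calculating clinical significance for the TFI as the primary outcome". The next sentence gives its inputs: "This was calculated using the mean pretest posttest score difference, the pre-intervention standard deviation, and a test-retest reliability coefficient of 0.78". The section cites the RCI method paper, and the TFI validation study for the reliability value. It writes out no formula, names no cut-off, and does not say that participants are classified or counted.

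The same section already plans a group effect size, Cohen's d, "calculated by dividing the differences in pre- and post-intervention means by the pooled standard deviations".

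The neighbouring sections do not fill the gap. For outcomes, Sample Characteristics plans only summaries: "The mean and standard deviation were reported for each outcome measure at each time point". The Statistical Analysis Plan section states the pilot's targets, "The study outcomes of interest were retention, feasibility, and effect size at post-intervention", and the handling of missing data, "Missing data were handled through multiple imputation using the Markov Chain Monte Carlo approach" and "For comparison purposes a completer's only analysis was also done", without mentioning the RCI. Its alpha of 0.05 refers to p-values. The one TFI threshold in the document is under Recruitment, "A tinnitus severity score of 25 or greater on the TFI indicating the need for an intervention". That is an entry criterion, not an outcome rule.

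**The concern.** A reliable change index asks whether one person's change is larger than measurement error in that person's two scores could plausibly produce. Its denominator is therefore an individual-level error. Putting a group mean over it mixes two levels: the result says nothing about any individual, and it is not a test of the mean, because the sample size does not enter.

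What is at stake is the information that a clinical-significance analysis is meant to add to an effect size: how many of the 32 participants reliably improved, how many did not, and whether any reliably worsened. Those counts cannot be worked out from the means and SDs that the plan reports. The study is also meant to shape the protocol of a larger trial, so an unclear definition for the primary outcome could be carried forward.

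**Working it through.** **Inputs from the document.** Reliability r = 0.78, the pre-intervention SD and the mean pre-post difference (Effect Sizes and Statistical Modelling); n = 32, one group (Study Design). The document gives no TFI mean, TFI SD, RCI value or RCI cut-off, so there is no planned figure to reproduce.

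**Assumptions.** The standard RCI formula; a cut-off of 1.96 (conventional, not stated in the plan); individual changes normally distributed with SD s between 0.7 and 1.1 SD_pre. The lower end is just above the 0.663 SD_pre that measurement error alone implies. In this section a positive change means improvement.

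**1. Denominator.** SD_pre × √(2 × (1 − 0.78)) = SD_pre × √0.44 = 0.663 SD_pre.

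**2. The literal index.** Mean change / (0.663 SD_pre) = 1.508 × (mean change / SD_pre). This is an effect size standardised by the baseline SD, multiplied by a constant.

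**3. Overlap with Cohen's d.** Let q = SD_post/SD_pre. The pooled SD is SD_pre × √((1 + q²)/2), so the literal index equals d × √((1 + q²)/2) / 0.663. For assumed q of 0.8, 1.0 and 1.2 this is 1.37, 1.51 and 1.67 times d. Given the reported means and SDs, a reader could derive the literal index without any further analysis.

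**4. The individual bar.** 1.96 × 0.663 SD_pre = 1.30 SD_pre. For an assumed TFI SD of 15 to 25 points, that is a change of 19.5 to 32.5 points.

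**5. Group value against individual counts.** For a mean change of m (in SD_pre), share improved = P(Z > (1.30 − m)/s) and share worse = P(Z < (−1.30 − m)/s).

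| m | Group value (m/0.663) | s | Improved | Of 32 | Worse |
|---|---|---|---|---|---|
| 0.8 | 1.21 | 0.7 | 23.7% | 7.6 | 0.1% |
| 0.8 | 1.21 | 0.9 | 28.9% | 9.3 | 1.0% |
| 0.8 | 1.21 | 1.1 | 32.5% | 10.4 | 2.8% |
| 0.4 | 0.60 | 0.7 | 9.9% | 3.2 | 0.8% |
| 0.4 | 0.60 | 0.9 | 15.9% | 5.1 | 2.9% |
| 0.4 | 0.60 | 1.1 | 20.7% | 6.6 | 6.1% |

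The group value does not move with the spread of individual changes, but the counts do. At m = 0.8 the share improved is about 24% to 32% (the unrounded upper value is 32.47%), or 8 to 10 of 32.

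**6. Precision.** The Wilson 95% interval for 8/32 is 13% to 42%, and for 0/32 it is 0% to 11%. The first interval is wider than the 24% to 32% range above. The illustration therefore shows that the group value cannot stand in for a count, not that a count would be precise.

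**The case against.** The strongest reply is that the plan names and cites an established per-participant method and lists the SD and reliability that the method needs. On that reading, mean is a slip, and the citation brings the formula and usual cut-off with it. This may well be right, and it limits the point: the document does not show that a group-level analysis was run, and a reader who infers that goes too far. The reply does not remove the point. The only numerator that the plan states is the mean, no other section corrects it, and no cut-off or participant classes are stated on either reading.

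Two other stronger readings are tempting. One is that the group value would be held against 1.96 and would hide real improvement. The plan applies no threshold to a group value, so this would be a misuse that it does not propose. The other is that the missing formula and cut-off leave the responder share wide open. Nothing in the document suggests a different formula or a looser cut-off. The three inputs are enough to infer the usual formula, and the two-sided alpha of 0.05, although stated for p-values, is more in keeping with 1.96 than with a one-sided value.

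It is also fair to say that this is a small uncontrolled pilot, and that the plan describes its data as openly available. If individual TFI scores are among them, the counts can still be produced. That lowers the severity and makes the correction easy.

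**Conclusion.** The point holds as a minor fix to a supportive analysis. As written, the RCI sentence yields mean change / (0.663 SD_pre), assuming the standard formula. That is close to a repeat of Cohen's d (1.37 to 1.67 times d for the assumed SD ratios) and says nothing about individual reliable change in either direction. In the illustration, one group value of 1.21 goes with about 8 to 10 of 32 participants reliably improved; this rests on the assumed normal changes, the assumed spread and the conventional cut-off, none of which the plan supplies.

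A reader might infer that the pilot's conclusions are undermined. The document does not support that: its outcomes of interest are retention, feasibility and effect size, and none of them depends on the RCI.

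**What to change.** Replace the mean difference with each participant's own difference and complete the definition, for example:

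> For each participant, RCI = (post TFI − pre TFI) / (SD_pre × √(2(1 − 0.78))), where SD_pre is the baseline sample SD; negative values mean improvement. Participants are classed as reliably improved (RCI ≤ −1.96), reliably worse (RCI ≥ 1.96) or unchanged. The number and percentage in each class are reported for completers, with Wilson 95% confidence intervals, and for the imputed data, classified within each imputation and then averaged, with the pooling method for the interval stated.

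The authors may prefer another cut-off but should state it. If a group value was intended, the plan should say so and should not present it as clinical significance.

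The cost is a few sentences and a short script on data already collected, plus a little work to pool the classes across imputations. There are two downsides: the intervals will be wide with 32 participants, and without a control group the counts cannot separate treatment effect from natural change. Both should be stated beside the results.
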